9.3 Storage and disposition of study treatment(s)

Scopolamine (and placebo) will be stored securely at the HRB-CRFG as per manufacturer's guidelines. Scopolamine (hyoscine hydrobromide) will be stored in Pharmacy Clinical Trials Unit (PCTU) as per manufacturer's storage instructions. Placebo will be stored in clinical area as per manufacturer's instructions. Active and control treatments will be prepared into infusions by an appropriately trained and delegated unblinded site team healthcare professional based in the HRB-CRFG as per institutions guidelines/applicable SOPs in a separate clinical area away from the blinded study personnel and participant treatment area. The unblinded staff member will not be involved in any patient assessments or data analysis. Infusions should be administered to the participant immediately with minimal delay. The entire contents of the infusion bag must be administered to the participant. Empty infusion bags and any unused product will be disposed of according to institutions guidelines/applicable SOPs.

An accurate and timely record of IMP & placebo inventory must be maintained through the duration of the trial (including receipt, dispensing, return if applicable and destruction of unused product). A temperature log must be maintained for documentation of appropriately IMP and placebo storage areas.

9.4 Preparation/Reconstitution of Dosage Form

Administration instructions and dose preparation instructions will be provided as per the IMP handling manual.

9.5 Accountability of the study treatment(s)

The study medication will be supplied by Martindale Pharmaceuticals, UK. Upon delivery, receipt of the products will be recorded by pharmacy staff and labels applied as described in IMP Handling Manual with products then transferred to the secure storage area. Unopened products which are unused by end-of-trial will be destroyed on site as per site destruction policies.

9.6 Assessment of compliance

In this study, interventions will be administered intravenously by the research team and thus treatment non-compliance will be low-risk. Non-compliance may result however from participants refusing further infusions after attaining an initial infusion(s), or asking for an infusion to be discontinued during an infusion.

The investigator is responsible for ensuring that the study treatment is administered in compliance with the protocol. Participant compliance will be assessed by maintaining dispensing records.

9.7 Overdose of Study treatment

It is deemed unlikely that an overdose will occur in this study, given the safeguards in place with careful preparation of each infusion. The Scopolamine drug will be prepared by approved study specific instructions as per the IMP Handling Manual to ensure appropriate preparation of the drug and accuracy of calculations performed as part of drug preparation. In the very improbable event of an overdose, the study participant will be monitored for any change in vital signs by the research team members. If adverse symptoms arise secondary to an overdose, local site policy will be followed in relation to management of any medical emergency. Infusions will be administered over a 15 minute period, with this controlled by use of a calibrated IV infusion pump. Thus, it is unlikely that an infusion will be administered in a time-frame of less than 15 minutes, however if this occurs and adverse symptoms arise, local policy will similarly be followed in relation to the management of a medical emergency.

9.8 Prior and concomitant therapy

All current medication, in addition to the study medication taken during the study will be recorded in the patient's notes. Medications will be documented at the point of consent, at Visit 2 with changes in treatment notes at every assessment appointment thereafter. Psychotropic medications prescribed over the previous six months will also be documented.

9.8.1 Permitted medications/non-investigational medicinal products

All medications including herbal treatments aside from those listed in section 9.8.2 are permitted. Standard of care will continue for all participants during this study.

9.8.2 Prohibited medications

The following medications are contraindicated during the randomised treatment period as they may potentially alter the pharmacokinetics of Scopolamine and any participants newly prescribed these medications at randomisation visit will be excluded from the trial prior to any infusion being administered.

- Physostigmine
- Biperiden
- Procyclidine
- Tricyclic Antidepressants with significant anticholinergic properties (e.g. Amitriptyline and Nortriptyline) that are causing the participant to experience anticholinergic side effects (e.g. blurred vision, constipation, urinary retention, cognitive difficulties).

Participants prescribed any of the above agents during the trial will not receive any further intervention (infusions of Scopolamine or placebo), however will be followed up for the remainder of the trial with data collected included in intention-to-treat analyses if one infusion and one follow-up assessment have been completed.

Participants cannot participate in any other IMP studies while participating in this study (Visits 2-7).

10. Safety reporting

Adverse events will be captured for all study participants from the time of consent for the duration of their participation in the study i.e. from the time of consent to their final study visit. A full AE review at each study visit will ensure that a complete evaluation of the safety and tolerability of the IMP is conducted.

All participants will have their heart rate and blood pressure measured prior to infusion and post-infusion to measure haemodynamic changes, with normal results (see section 8.4.4.1) required post-infusion prior to the participant completing their visit (minimum 90 min monitoring period).

If the readings have not returned to normal within this required 90-minute monitoring period a further period of monitoring will be conducted. A treating investigator must assess and decide if medical intervention is required based on their clinical judgement. Additionally, the PRISE questionnaire (this is optional for participants) will be used where participants agree to document other adverse effects prior to participants completing their clinical visits 2, 3, 4, and 5 (see Section 8.5). All adverse events will be reported to the Sponsor on the AE case report.

10.1 Definitions

10.1.1 Adverse event (AE)

Any untoward medical occurrence in a patient or clinical trial participant administered a medicinal product and which does not necessarily have a causal relationship with this treatment.

An adverse event can therefore be any unfavourable and unintended sign (including an abnormal laboratory finding, for example), symptom or disease temporally associated with the use of a medicinal product, whether or not considered related to the medicinal product.

Each individual unintended sign, symptom or disease is considered a separate adverse event unless an overarching diagnosis can be made for a collection of signs or symptoms that are clinically linked and temporally related. The overarching diagnosis should be as specific as possible, using all available clinical data.

All events must undergo an assessment to determine if any of the seriousness criteria are met and each event must be reported to the Sponsor.

10.1.2 Adverse Reaction (AR)

All untoward and unintended responses to a medicinal product related to any dose. The phrase 'responses to a medicinal product' means that a causal relationship between a study medication and an AE is at least a reasonable possibility, i.e., the relationship cannot be ruled out. All cases judged by either the reporting medically qualified professional or the sponsor as having a reasonable suspected causal relationship to the study medication qualify as adverse reactions.

10.1.3 Serious Adverse Event (SAE) or Serious Adverse Reaction (SAR)

Any untoward medical occurrence or affect that at any dose meets one or more of the following criteria:

- results in death,
- is life-threatening*,
- requires hospitalisation (defined as >24 hour hospital stay or admission to inpatient hospital area) or prolongation of existing hospitalisation,
- results in persistent or significant disability or incapacity,
- is a congenital anomaly or birth defect
- is medically important**

* This refers to an event in which the participant was at risk of death at the time of the event; it does not refer to an event which hypothetically might have caused death if it were more severe.

** Some medical events may jeopardise the participant or may require an intervention to prevent one of the above characteristics/consequences. Such events (hereinafter referred to as 'important medical events') should also be considered as 'serious' in accordance with the definition.

10.1.4 Suspected unexpected serious adverse reactions (SUSAR)

An adverse reaction, the nature or severity of which is not consistent with the applicable product information (i.e. section 4.8 of the summary of product characteristics).

10.1.5 Severe Adverse Event

The term 'severity' is used here to describe the intensity of a specific event. This has to be distinguished from the term 'serious'.

10.2 Evaluation of AEs and SAEs

The investigator or delegate will report all AEs and SAEs to the Sponsor as outlined in section 10.3, except for those identified as outcomes identified below.

10.2.1 Events exempt from reporting

10.2.1.1 Cannulation related

The following commonly experienced events related to cannulation are exempt from AE reporting if they are reported at the site of cannulation and are deemed non-clinically significant by a study investigator.

- (a) Discomfort
- (b) Small haematoma
- (c) Bruising
- (d) Transient light headedness
- (e) Irritation to plaster/dressing used over or around cannulation site.

If the nature or severity of the event exceeds what is commonly experienced or if the event is deemed clinically significant by the investigator the event should then be reported as an AE. Events related to cannulation must be reported as SAEs/SARs if they meet one or more of the seriousness criteria as defined above.

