7.3.2 Secondary Endpoints

1. Remission of depressive episode measured with the HDRS at Visit 6 compared to Visit 3.
2. Response to a depressive episode measured with the HDRS at Visit 6 compared to Visit 3.
3. Reduction of depressive symptoms (MADRS) at Visit 6 compared to Visit 3.
4. Improvement in objectively measured overall functioning (GAF) at Visit 6 compared to Visit 3.
5. Reduction in depressive symptoms as measured using the POMS after all IV infusion visits compared to before IV infusions at the same visit (Visits 2, 3, 4, 5).
6. Response and remission data measured with the HDRS at Visit 7 compared to pre-randomisation HDRS scores at Visit 3.
7. Reduction in subjectively measured mood symptoms using the POMS at follow-up visits (Visits 6 and 7) compared to pre-randomisation.
8. Reduction in depressive symptoms, measured with the MADRS at Visit 7 compared to MADRS scores at Visit 3.
9. Improvement in global functioning, measured with the GAF at Visit 7 compared to pre-infusion GAF scores at Visit 3.
10. Psychiatric inpatient admissions due to depressive episodes over the duration of the study.
11. Antidepressant medication usage or change in antidepressant medication dose due to depressive episodes over the duration of the study.
12. Adverse events over the duration of the study.
13. Post infusion side effects at all 3 IV treatment visits: Bradycardia, Hypotension, Dizziness and Sedation (Visits 3, 4 and 5)
14. Occurrence of a hypo (manic) episode over the duration of the study.
15. Improvement in motor processing, visual and spatial memory at Visit 6 compared to initial scores measured at Visit 2 or Visit 3 as measured on CANTAB.

8. Trial Design

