17.4.1.4 Risks and hazards secondary to IV Scopolamine infusion

AEs that have occurred have been transient in nature (<3 hours) and have included light headedness, sedation, a transiently reduced heart rate and blood pressure (requiring no intervention) and the recognised anticholinergic adverse effects of dry mouth and blurred vision (Drevets and Furey, 2010; Furey and Zarate, 2013).

Pulsed IV administration has not been associated to date with potential AEs noted with high oral dosages including delirium, (hypo)mania, psychosis or disorientation (Furey and Zarate, 2013).

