13. Change in motor processing, visual and spatial memory (3 categorical variables) at Visit 6 compared to Visit 2 based on the Cambridge Neuropsychological Test Automated Battery (CANTAB) battery of tests.

SCOPE-BD NUIG-2017-002, Statistical Analysis Plan Version 1, 19/03/2024

14. Occurrence of a hypo (manic) episodes at visits 3, 4, 5, 6 or 7, as defined by a score of >6 on the Young Mania Rating Scale (YMRS).

15. Occurrence of other adverse effects as observed on monitoring of vital signs, reported by participants or measured utilising the Patient Rated Inventory of Side Effects (PRISE) questionnaire

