## 14 Safety Analyses

The results of clinical monitoring including blood pressure or heart rate changes, and AEs secondary to phlebotomy or cannulation will be examined between the groups. Adverse events will be coded according to the Medical Dictionary for Regulatory Activities (MedDRA). The incidence of treatment-emergent adverse events will be summarized by system organ class (SOC) and preferred term.

Safety data will be presented primarily in a descriptive fashion. The small sample size and likely low adverse event rates will mean any inference is likely underpowered to detect a range of meaningful differences.

Blinded data will be presented to the DSMB for safety evaluation to coincide with scheduled DSMB meetings.

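### Mild transient light-headedness can be left out of the AE record as a cannulation event, although the protocol names it as a scopolamine effect and makes post-infusion dizziness a secondary endpoint

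*Protocol*

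**What the plan says.** Protocol 10.2.1.1 names five common cannulation-related events, including "d) Transient light headedness". They "are exempt from AE reporting if they are reported at the site of cannulation and are deemed non-clinically significant by a study investigator". An override follows: "If the nature or severity of the event exceeds what is commonly experienced or if the event is deemed clinically significant by the investigator", it is reported as an AE, and anything that meets a seriousness criterion is reported as serious.

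Elsewhere the protocol treats the same or a closely related symptom as a drug effect and as an outcome:

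- Protocol 17.4.1.4 says that the AEs seen with IV scopolamine lasted under 3 hours and "have included light headedness, sedation, a transiently reduced heart rate and blood pressure".
- Protocol 7.3.2 item 13 makes post-infusion side effects a secondary endpoint: "Bradycardia, Hypotension, Dizziness and Sedation (Visits 3, 4 and 5").
- Protocol 8.12.1.2 and SAP 5.2.2 do not carry item 13 by name. What remains is the general item 15: "Occurrence of other adverse effects as observed on monitoring of vital signs, reported by participants or measured utilising" the optional PRISE questionnaire.
- SAP 14 states that "AEs secondary to phlebotomy or cannulation will be examined between the groups". SAP 14.3.3 plans no other AE assessment.

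**The concern.** Every infusion is preceded by a cannulation, and under protocol 17.4.1.3 the cannula serves the infusion and comes out before discharge. A light-headed spell during or after the infusion therefore also follows a cannulation. Being transient does not help to tell the two causes apart, because protocol 17.4.1.4 describes the drug effect as transient too.

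The site condition does not separate them either. Read literally, it can never be met by light-headedness, so item (d) does nothing. Read as presumably intended, item (d) covers light-headedness thought to come from the needle, with no limit on when it starts.

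What is at stake is the tolerability comparison. Safety is part of the primary objective (protocol 7.1), and the tolerability of three repeated infusions is secondary objective 2 (protocol 7.2). Mild, short-lived effects are what such a comparison has to count, and they are the ones that item (d) can leave out. The efficacy analysis is not affected.

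**Working it through.** The plan states no rate for light-headedness or dizziness, so there is no figure to reproduce. The check sets the sections side by side and then adds an illustration.

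**Step 1. Where exempted events go (protocol 10.2.1.1 to 10.2.1.5)**

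| Exemption | Time window | Alternative record named |
|---|---|---|
| 10.2.1.1 cannulation | none | none |
| 10.2.1.2 scopolamine infusion | 90 minutes after infusion | study outcome form |
| 10.2.1.3 mood symptoms | none | case report forms |
| 10.2.1.4 psychotropic changes | none | case report forms |
| 10.2.1.5 psychometric scores | none | case report forms |

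The cannulation exemption is the only one of the five that names no other place for the event.

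**Step 2. Where each part of 7.3.2 item 13 could be picked up**

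| Effect | Named source |
|---|---|
| Bradycardia, hypotension | Compulsory vital signs (protocol 8.4.4.1), summarised in SAP 14.6 |
| Sedation | Drowsiness, under 10.2.1.2 and as a compulsory VAS item (protocol 8.5) |
| Dizziness | No compulsory routine item. General AE assessment before, during and after infusion (protocol 8.3.5), optional PRISE, and an AE form tied to dizziness only when consent is withdrawn during or just after an infusion (protocol 8.11) |

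Dizziness thus depends mainly on the general AE record, to which item (d) applies. The documents do not say that dizziness and light-headedness are the same. Treating them as one symptom group is a reasonable assumption of this review.

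**Step 3. Effect on the recorded difference (illustration; all rates are assumptions)**

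Inputs: 25 participants per arm (protocol 8.2.1); true proportions affected pS on scopolamine and pP on placebo; f, the share of affected participants whose light-headedness is classed as cannulation-related and exempted, taken as equal in both arms because staff are blinded.

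Recorded difference = (1 − f) × (pS − pP).

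With pS = 0.40 and pP = 0.10, the full record would show 25 × 0.40 = 10 against 25 × 0.10 = 2.5 participants:

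| f | Recorded difference | Expected participants (scopolamine vs placebo) |
|---|---|---|
| 0 | 0.30 | 10 vs 2.5 |
| 0.25 | 0.225 | 7.5 vs 1.88 |
| 0.50 | 0.15 | 5 vs 1.25 |
| 0.75 | 0.075 | 2.5 vs 0.62 |
| 1 | 0 | 0 vs 0 |

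Range: with pS from 0.20 to 0.60 and pP from 0.05 to 0.10, the full-record difference runs from 0.20 − 0.10 = 0.10 to 0.60 − 0.05 = 0.55. At f = 0.50 it runs from 0.05 to 0.275.

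Two limits apply:

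- Equal thinning leaves the ratio of proportions unchanged (0.40/0.10 = 0.20/0.05 = 4). It shrinks the difference and the counts.
- Only misattribution does harm. If the 10% were needle-related in both arms and exactly those participants were exempted, the record would show 0.40 − 0.10 = 0.30 against 0.10 − 0.10 = 0, and the difference would stay at 0.30.

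**The case against.** The strongest reply is that the exemption is narrow. The event must be related to cannulation, not merely follow it, and must be judged not clinically significant; the override then catches anything unusual. Causality is a separate judgement under protocol 10.2.3. Dizziness and light-headedness are not among the five effects exempted in 10.2.1.2, so when attributed to the infusion they are ordinary AEs. Protocol 10.3.1 calls for AEs to be recorded regardless of attribution, and protocol section 10 requires a full AE review at each visit. All of this stands. It confines the problem to mild, transient episodes that an investigator puts down to the needle. It does not remove the problem, because the protocol gives the investigator no criterion for telling those episodes from the drug effect.

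Some stronger readings are tempting, and the documents do not support them:

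- A reader might infer that dizziness is not collected at all. The case report forms are not among the documents, and 10.2.1.2 does not say that the outcome form holds only its five effects. The text shows only that no compulsory dizziness item is named.
- A reader might see SAP 14 as contradicting 10.2.1.1. Only minor cannulation events are exempt; clinically significant ones stay reportable and can be compared between groups.
- A reader might think that sedation is lost as well. Drowsiness on the outcome form and on the compulsory VAS largely covers it.
- A reader might take an excess on scopolamine as established. Protocol 17.4.1.4 makes it plausible but gives no comparative rate.

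Blinding is a fair point against differential misattribution between the arms. It does not rescue the recorded difference, since equal misattribution is enough to shrink it.

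**Conclusion.** The point holds as a gap in recording. Item (d) has a condition that does not fit the symptom, no time limit and no fallback form, and it concerns a symptom that the protocol names as a drug effect and that is closely related to a secondary endpoint. Mild drug-related episodes attributed to cannulation can be left out of the AE record; whether any will be cannot be told from the documents. If the true rate is higher on scopolamine and misattribution is equal across arms, the recorded difference falls by the exempted share, for example from 30 to 15 percentage points at assumed rates of 40% and 10% with half exempted. The direction rests on a true excess on drug and on some misattribution of drug-caused episodes; the size rests entirely on assumed rates. Safety reporting is descriptive and the plan itself says that safety inference is likely underpowered, so no planned test is invalidated. The change is still worth making, because it is cheap and the affected comparison belongs to the trial's stated objectives.

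**What to change.** 1. In protocol 10.2.1.1, delete item (d), or limit it to light-headedness that starts and resolves before the infusion begins.
2. At Visits 3, 4 and 5, record dizziness or light-headedness (yes/no) for every participant on the study outcome form, whatever the attribution, with onset time relative to cannulation and to the start of infusion. If the form already has such an item, say so in the protocol.
3. Carry protocol 7.3.2 item 13 into protocol 8.12.1.2 and SAP 5.2.2, and add counts and percentages by arm and visit to SAP 14.
4. Designate drowsiness on the outcome form and the VAS as the measure of sedation; no new item is then needed.

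The cost is one line in the protocol, one item with a time field on an existing form, and one table. The downside is a few more minor events recorded. The change concerns recording only and leaves clinical management as it is. Where visits have already taken place under the present rule, the SAP table can still be added, and the report should state that mild light-headedness may be under-recorded.

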10.2.1.2 Scopolamine infusion related

The following events are considered expected, transient side effects of scopolamine therapy and are therefore exempt from safety reporting if they occur in the 90 minutes post IMP infusion (visit 3, visit 4 or visit 5). These events will be captured on a study outcome form.

- (a) Drowsiness
- (b) Blurred vision
- (c) Dry mouth
- (d) Thirst
- (e) Urinary retention

The above occurrences are considered Adverse events and therefore reportable if any of the following occur:

- medical intervention or treatment
- prolonged monitoring in addition to the 90 minutes post infusion required by the protocol
- deemed medically significant by an investigator
- cessation of the study drug (current or subsequent infusions)

These events must be reported as SAEs/SARs if they meet one or more of the seriousness criteria.

